5.3 All-Trans Retinoic Acid (Tretinoi)

Description: Tretinoi is a retinoid derived from naturally occurring all-trans-retinol (Vitamin A1). The compound is formed *in vivo* from retinol and can be detected at nanogram levels in normal and human plasma (40). Tretinoi binds to serum albumin, is not stored in the liver, and probably enters cells by diffusion. In the cytoplasm, Tretinoi binds to cellular retinoic acid binding proteins (CRABPs) and is transported to the nucleus (41), where it is released and binds to nuclear RARs. The signaling pathway after ligand-RAR binding is poorly characterized. Isomers of tretinoi including 9-cis RA and 13-cis RA, as well as vitamin A, β-carotene and various synthetic retinoids, have been clinically studied for anticancer and /or cancer chemoprevention activity.

Other names: Vesanoid ®

Drug supply and distribution: Tretinoi is manufactured and distributed by Hoffman LaRoche.

How supplied: 10 mg capsules

Storage: Store at 15 to 30 degrees Celsius (59 to 86 degrees F) and protect from light.

Precautions: Tretinoi is teratogenic and fetotoxic in rats at doses 1000 and 500 times the topical human dose, respectively. Tretinoi is contraindicated in persons sensitive to parabens, vitamin A, and other retinoids.

Mechanism of Action: Numerous reports have documented tretinoi induced differentiation of APL cell in vitro. Retinoids are known to induce granulocytic differentiation and inhibition of clonal growth in the HL-60 cell line (42). Both tretinoi and 13-cis-RA isomers are active in HL-60 at approximately 10-6 M. Response to retinoids in other leukemia cell lines has been less consistent. KG-1 cells showed growth inhibition at 10-9 M but exhibited no morphologic, histochemical or functional differentiation (43). K-562 cells treated with 10-6 M tretinoi displayed a normal growth pattern. U937 cells underwent monocytoid differentiation at 10-6 M and THP-1 cells showed functional (but not morphologic) differentiation at 10-9 M (43). Tretinoi has produced dramatic clinical benefit in patients with APL, and as a single agent has significantly survival in this disease (44). The drug is commercially approved for this indication.

6.1 CRITERIA FOR SUBJECT ELIGIBILITY

6.2 Subject Inclusion Criteria

- Diagnosis of a myelodysplastic syndrome according to the FAB classification system, which has been confirmed at MSKCC
- Age greater than or equal to 18 years
- IPSS score of greater than or equal to 0.5.
- Performance Status of ≥ 60 % (Karnofsky)
- Serum total bilirubin ≤ 2.5
- SGOT and SGPT should be ≤ 2 times the upper limit of normal.
- Serum creatinine should be $\leq 1.5 \times$ ULN, or 24 hour creatinine clearance must be ≥ 60 cc/min.
- Negative pregnancy test for women with child-bearing potential.
- Female patients with child-bearing potential or male patients who are sexually active must agree to use an accepted form of contraception.
- Signed informed consent
- Transplant ineligible prior to therapy
- Prior 5-azacytidine recipients are eligible regardless of prior response to 5-azacytidine.
- Prior decitabine recipients must have had a response (HI or better per IWG Response Criteria), followed by POD (POD after decitabine was discontinued).
- Patients will be eligible for entry if they have IPSS Intermediate-1, Intermediate-2 or High Risk disease.

6.3 Subject Exclusion Criteria

- Pregnant or lactating women. Patients with childbearing potential will be required to practice an accepted mode of birth control.
- Cytotoxic chemotherapy or radiotherapy within 4 weeks of starting treatment
- Experimental therapy within 4 weeks of starting treatment
- Medical condition which, in the opinion of the treating physician, would put the patient at excessive risk of toxicity from the treatment
- Inability to adhere to treatment or monitoring schedule
- Unwillingness to provide research specimens as outlined in the protocol
- Presence of another malignancy which will likely require systemic chemotherapy within 4 months of starting decitabine and tretinoin.
- Decitabine refractory MDS
- Allergy to parabens, vitamin A, or retinoids

7.0 RECRUITMENT PLAN

The study will be conducted at MSKCC. The study will accrue approximately 45 evaluable patients. Approximately 200 new patients with a diagnosis of MDS are seen annually by physicians on the Hematology, Leukemia and Allogeneic Bone Marrow Transplant Services. It is estimated that 2.0 years will be required to accrue ~ fifty eligible patients. Efforts will be made to enroll women and minorities onto this trial. It is expected that the sex and racial breakdown of patients entered into this trial will reflect the overall referral patterns seen at MSKCC. However, because of the small number of patients entered into this trial, an absolutely representative cohort may not be accrued.

8.1 PRETREATMENT EVALUATION

8.2 Pre-study Evaluation (Eligibility Assessment)

Eligibility evaluations to be performed within 30 days of starting therapy with decitabine and tretinoin will include the following:

- Bone marrow aspirate for histology, cytogenetics, flow cytometry, and a bone marrow biopsy.
- Baseline bone marrow aspirate will also be obtained for research studies. Therefore patients will be consented prior to their baseline bone marrow procedure.
- Physical exam with review of systems, medical history, Karnofsky performance status, , FAB classification, history of prior medications, prior MDS treatments, history of transfusions requirements for two months prior to registration.
- Determination of elements of IPSS (bone marrow aspirate and complete blood count), which produces IPSS score of 0.5 or greater.
- Electrocardiogram (EKG)
- Comprehensive metabolic panel, CBC with differential and smear review, reticulocyte count, pregnancy test for women with child-bearing potential.
- Assessment of ability of the patient to comply with the requirements of the protocol.

8.3 Baseline evaluations

Baseline evaluations to be performed within 7 days of starting therapy with decitabine and tretinoin will include the following:

- Interim medical history including review of systems, height, weight, vital signs, and calculation of body surface area, medications, transfusion requirements, Karnofsky performance status.

- Comprehensive metabolic panel, CBC with differential and smear review, reticulocyte count, PT, PTT, pregnancy test for women with child-bearing potential.
- Patients must meet all eligibility criteria at the time of the baseline evaluation.

9.0 TREATMENT/INTERVENTION PLAN

Eligible patients will receive Decitabine at a dose of 20 mg/m² daily for 5 days as an outpatient and will receive a total dose per cycle of 100mg/m². Beginning on day 10 of each cycle, patients will self-administer tretinoin for 10 days (See Figure 1.1). Treatment will be recycled every 28 days. The tretinoin dose will be escalated within the range of 45 mg/m²/day to 85 mg/m²/day to determine the MTD within that range. Although unlikely, if DLT is seen in two patients at 45 mg/m²/day, a dose de-escalation scheme will be employed to explore the safety of 30 mg/m²/day and 15 mg/m²/day.

The tretinoin dose escalation will proceed as follows: Three patients will receive 45 mg/m²/day given over two doses each day (standard dose used for acute promyelocytic leukemia alone or in combination with cytotoxic chemotherapy). If no dose-limiting toxicity is observed (see section 11.5 for definition of DLT) after completion of one cycle of therapy, three additional patients will receive 65 mg/m²/day given over two doses each day. If no dose-limiting toxicity is observed after one cycle of therapy, three additional patients will receive 85 mg/m²/day given over two doses each day. Doses above 85 mg/m²/day will not be tested in this trial. Based on prior studies with tretinoin monotherapy, toxicity that is unacceptable for the planned patient population is expected at or beyond a daily dose of 90 mg/m², and biological effects of tretinoin can be expected as doses lower than 85 mg/m²/day. A DLT in one patient at any of the three dose levels tested will require the addition of three patients at that dose level. If DLT recurs in a second patient (2/6), the next lower dose level will be considered the MTD. If no DLT is seen amongst the three patients treated at the highest tretinoin dose tested (85 mg/m²), an additional 3 patients will be treated at this dose level to confirm this dose as the maximal tolerated dose. If required, the tretinoin dose de-escalation schema will proceed as follows: If two patients experience DLT at 45 mg/m²/day during the first cycle of therapy, and the toxicities are likely attributable to tretinoin, patients will be enrolled to receive tretinoin at a dose of 30 mg/m²/day, and 15 mg/m²/day if 30 mg/m²/day is not tolerated (if 2/6 patients experience DLT). If 15/mg/m² is not tolerated (2/6 patients experience DLT), the study will be terminated due to excessive toxicity of the regimen.

Once the MTD is established, patients will be accrued to the phase II portion of the study which will evaluate the efficacy of decitabine in combination with the MTD of tretinoin. The phase II study will have a 2-stage design. In the first stage of this design, twenty seven patients will be treated. Patients treated at the tretinoin MTD (6 patients) in the phase I portion of the study will be carried over and counted among the patients in stage 1. If two or fewer responses (CR or PR) are seen among the first 27 patients, the study will be closed for lack of efficacy. If at least three responses (CR or PR) are seen in the first stage, then an additional 13 patients will be accrued in the second stage. To qualify as a non-responder, patients must undergo disease re-evaluation studies (bone marrow and complete blood counts) after completing four cycles of therapy.

Treatment will be recycled every 28 days, provided there is adequate recovery from non-hematologic toxicities. The start of cycle #1, or subsequent cycles may be delayed for up to 2 weeks in the event of 1) uncontrolled infection, or 2) other abnormalities that would preclude patient eligibility (see sections 6.1 and 6.2).

Patients will receive treatment for a minimum of 4 cycles, barring removal for progression of disease or excessive toxicity. Patients must achieve hematologic improvement (HI) or Bone Marrow PR/CR by the completion of cycle #6. Patients achieving HI or bone marrow PR/CR by the completion of cycle #6 may receive up to a total of 10 cycles of therapy, barring excessive toxicity. If the best response after cycle #6 is Stable Disease, these patients will be removed from study. Patients in the phase I study will continue at the study entry dose. Treatment will be interrupted for grade III or IV non-hematologic toxicity attributable to tretinoin or decitabine. Therapy may be resumed with the next cycle of treatment as long as the toxicity has decreased to < grade 2 within 8 weeks of the last treatment administration. However, these patients will receive a 25% dose reduction in tretinoin or decitabine (which ever treatment is suspected or both if the attribution is unknown) when treatment resumes. All patients will be followed for Serious Adverse Events (SAEs) for 30 days after completion of the last cycle of therapy (each cycle is 28 days).

Effects of decitabine and tretinoin on markers of differentiation and apoptosis, and on the methylation and expression of various genes will also be assessed.

Myeloid growth factors will only be allowed in the setting of febrile neutropenia according to established guidelines for use (45).

10.1 EVALUATION DURING TREATMENT

10.2 Safety Monitoring:

Weekly while on study: Complete blood count (including differential)

Within 7 days of starting each cycle: CBC, Comprehensive metabolic panel, pregnancy test for patients with child-bearing potential, physical exam, assessment of performance status, medications and adverse events. Patients will be asked to maintain a symptom diary each cycle, which will be reviewed prior to starting each subsequent cycle. Patients will keep a tretinoin administration log, which will be reviewed with the patient. A pill count will be performed and correlated with the patient's tretinoin administration log to assess compliance with tretinoin administration. Physical exam and toxicity assessments may be required more frequently if clinically indicated.

10.3 Tests for Disease Response:

Complete blood count with differential and smear review prior to start of all treatment cycles.

Bone marrow aspirate and biopsy after even-numbered cycles (eg., 2, 4, 6, etc). Bone marrow aspirate studies for disease assessments will include flow cytometry, cytogenetics, and histochemistry.

10.4 Research Samples:

Research samples will be obtained on patients treated in the phase I and the phase II portion of this study at the following time points:

- (1) Prior to treatment (during the screening period when screening baseline bone marrow and bloodwork is obtained), blood (30 cc in heparin) and bone marrow aspirate (10 cc in heparin) will be obtained.
- (2) During cycle #1 and cycle # 2, on days 10 and 19, blood (30 cc in heparin) will be obtained for research purposes only (blood to be drawn with weekly routine blood work).
- (3) During cycle #1 only, on days 10 and 19, bone marrow aspirate (10 cc in heparin) will be taken for research purposes only.
- (4) At the time of scheduled disease assessments done after cycles 2 and 4, blood (30 cc in heparin) and bone marrow aspirate (10 cc in heparin) will be obtained.

10.5 Research Tests:

The following research studies will be performed at the time points indicated in 10.3 when feasible:

- (1) Bone marrow aspirate and peripheral blood mononuclear cells will be assessed for the extent of DNA methylation using array-based whole genome methylation analysis(NimbleGen) (46). The expression and methylation status of specific genes will be analyzed, focusing on, but not necessarily restricted to the following genes involved in the TGFB signaling pathway: p57, p 21, p73, p15INK4b, TGF β RII, RAR β , and JunB.
- (2) Bone marrow aspirate and peripheral blood mononuclear cells will be analyzed using gene profiling (Affymetrix) which will be performed by the Core Facility Laboratory.
- (3) Bone marrow aspirates and peripheral blood mononuclear cells will be analyzed by flow cytometry for evidence of differentiation using fluorescein isothiocyanate (FITC) - conjugated or phycoerythrin (PE)-conjugated monoclonal antibodies: CD16, CD11b, CD33, CD13, HLA-DR, CD34, CD45 and CD14. Combinations to be examined to assess for differentiation include CD33-PE and CD34-FITC, CD33-PE and CD11b-FITC, CD13-PE and CD34-FITC or CD11b-PE and CD34-FITC. Apoptosis will be assayed using flow cytometry and dual staining with Annexin V-PE and 7-AAD.

11.1 TOXICITIES/SIDE EFFECTS

11.2 Expected Side Effects of Decitabine

Common – Myelosuppression, nausea, vomiting.
Uncommon – Diarrhea, fever, anorexia, abdominal pain, mucositis, alopecia.
Rare – Death.

11.3 Expected Side Effects of Tretinoin

Common – Headache; dryness, scaling or flaking of skin; dry mouth and mucous membranes; cracking of lips; hyperlipidemia.
Uncommon – Increase in hepatic transaminases; hypercalcemia; nausea and vomiting;
Rare – Pancreatitis

11.4 Adverse Event Reporting

Adverse events will be followed after the patient has received their first dose of therapy on this trial, and will continue until 30 days after the completion of the last cycle of therapy. Toxicity will be graded and recorded using the NCI Common Toxicity Criteria version 2.0, to allow the use of the “leukemia” scale for grading hematologic toxicity.

Clinically significant adverse events will be noted and compared to the baseline condition. Adverse events that will be noted will include expected side effects, and any other clinically significant symptom or laboratory value. An assessment will be made concerning the severity of the event, and if the event appears to be related to the study drug(s). Adverse events, toxicity grading, and attributions will be recorded in the CRDB by the RSA after review of the data by the Principal Investigator. Hematologic toxicity will be graded using the “leukemia” grading scale in the NCI CTC version 2.0.

11.5 Serious Adverse Event (SAE) Reporting

An SAE is defined as any adverse effect occurring in a patient receiving the study drug(s) that results in the following:

Memorial Sloan Kettering Cancer Center
[name]
[name]

- Death
- A life-threatening illness or abnormality
- Hospital admission or prolongation of pre-existing hospitalization
- Persistent or debilitating disability
- Birth defect

Please refer to Section 17.2 and 17.2 for further SAE reporting guidelines.

11.5 Establishment of Maximum Tolerated Dose (MTD)

In the phase I portion of this study, the MTD of tretinoin will be determined (within the range of 15 mg/m² - 85 mg/m²) when given in combination with decitabine. At least three patients will be treated at each dose level, starting with 45 mg/m²/day, which is 30% of the MTD (in a phase I MTD of tretinoin monotherapy in MDS patients, the MTD was 150 mg/m²/day when given daily for 6 weeks (34)). Additional dose levels will be tested as follows: 65 mg/m²/day and 85 mg/m²/day.

A dose-limiting toxicity is defined as a grade III or IV non-hematologic toxicity (NCI CTC, ver. 2.0). If at any dose level one patient experiences grade III or IV non-hematologic toxicity (according to the NCI CTC version 2.0) attributable to tretinoin, three additional patients will be added to that dose level. If a second patient experiences grade III or IV non-hematologic toxicity, the dose level below will be considered the MTD, which is defined as the dose level below that which produces Grade III/IV non-hematologic toxicity in $\geq 33\%$ of patients.

If a DLT is experienced at 45 mg/m²/day and is attributable to tretinoin, a dose de-escalation schema will be employed (see section 9.0) to determine the MTD below 45 mg/m²/day.

If no DLT is seen after the 85 mg/m²/day dose level is complete, the phase II portion will proceed using tretinoin at a dose of 85 mg/m²/day. However, once the MTD is established, a total of 6 patients will be treated at that level to confirm the MTD before proceeding to the phase II portion of the study.

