1.0 PROTOCOL SUMMARY AND/OR SCHEMA

TITLE: Phase I/II Study of Decitabine and All-Trans Retinoic Acid (Tretinoiin) for Patients with Myelodysplastic Syndromes

OBJECTIVE: To determine whether the combination of decitabine with tretinoiin is safe and efficacious in the treatment of Myelodysplastic Syndromes.

PATIENT POPULATION: Adults (greater than 18 years) with a confirmed diagnosis of MDS (based on the FAB MDS diagnostic criteria (1)) and an International Prognostic Scoring System (2) score of 0.5 or greater (IPSS Intermediate-1, Intermediate-2, and High-Risk categories. For IPSS schema, see Appendix 1).

STUDY DESIGN: This is a single-center, open label, phase I/II study of the combination of decitabine (DAC) and All-Trans Retinoic Acid (Tretinoiin) in patients with Myelodysplastic Syndromes.

STUDY DRUG AND DOSE: Eligible patients will receive decitabine intravenously at a dose of 20 mg/m² daily for five days for a total dose per cycle of 100 mg/m². Decitabine will be administered as an outpatient at MSKCC. Beginning on day 10 of each cycle, patients will receive tretinoiin orally for 10 days as an outpatient (See Figure 1.1 for study design schema). Three successive tretinoiin dose levels will be evaluated: 45 mg/m²/day, 65 mg/m²/day, and 85 mg/m²/day given over two doses each day. A standard dose escalation scheme will be followed with cohorts of 3 to 6 patients treated at each dose level (section 14.0). A dose-limiting toxicity is defined as in section 11.5. If a DLT is seen at 45 mg/m²/day, a dose de-escalation schema will be applied (See section 9.0). If no DLT is seen amongst the three patients treated at a dose under consideration for MTD, then an additional 3 patients will be treated at this dose level to confirm this dose as the maximal tolerated dose.

The phase II study will have a 2-stage design. In the first stage of this design, twenty seven patients will be treated. Patients treated at the tretinoiin MTD (6 patients) in the phase I portion of the study will be carried over and counted among the patients in stage 1 of the phase II portion of the study. If two or fewer responses (CR or PR) are seen among the first 27 patients, the study will be closed for lack of efficacy. If at least three responses are seen in the first stage, then an additional 13 patients will be accrued in the second stage.

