4.1 OVERVIEW OF STUDY DESIGN/INTERVENTION

4.2 Design

This is a phase I/II study designed to evaluate the safety, biologic effects, and preliminary clinical efficacy of the combination of decitabine and tretinoin. Approximately 45 eligible patients with a myelodysplastic syndrome will receive the combination of decitabine and tretinoin. Decitabine will be administered at a dose of 20 mg/m²/day for five days every 4 weeks. Tretinoin will be administered from days 10-19 of each cycle in escalating doses to determine the MTD of Tretinoin in combination with decitabine.

The initial dose level will be 45 mg/m²/day, which is 30% of the MTD for Tretinoin in MDS patients (MTD = 150 mg/m²)(34), and is a dose that has been shown to produce apoptosis in non-M3 AML(23), and differentiation in APL. This is also the standard dose of tretinoin that has been administered safely to patients with acute promyelocytic leukemia in combination with cytotoxic chemotherapy. Three dose levels will be tested, with the maximum dose being 85 mg/m²/day. The rationale for this design is that tretinoin given at doses of 90 mg/m²/day or greater is more likely to produce side effects (primarily skin and mucosal toxicity) that we wish to avoid in this generally elderly patient population. Also, decitabine is expected to induce myelosuppression, and infection risk may be increased by compromised mucosal integrity. If 2 patients experience DLT at 45 mg/m²/day, a dose de-escalation scheme will be employed to determine the MTD below 45 mg/m²/day. Once the MTD is established, additional patients (to equal 6 patients) will be treated to confirm the MTD. If dose escalation proceeds to 85 mg/m²/day, and no DLT is seen in three patients, an additional 3 patients will be treated at this dose level to confirm this dose as the maximal tolerated dose. Once the tretinoin MTD is determined, the phase II portion of the study will proceed with tretinoin at the MTD in combination with decitabine.

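### The phase I rules conflict: after one DLT at 45 mg/m²/day some sections de-escalate and others add patients at that dose, and attribution and the DLT window are handled unevenly

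*Combined protocol and SAP*

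**What the plan says.** **Trigger at 45 mg/m²/day.** Two sections act on a single event:
- Section 1.0: "If a DLT is seen at 45 mg/m²/day, a dose de-escalation schema will be applied".
- Section 11.5 (Establishment of MTD): "If a DLT is experienced at 45 mg/m²/day and is attributable to tretinoin, a dose de-escalation schema will be employed".

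Three sections require two patients:
- Section 4.2: "If 2 patients experience DLT at 45 mg/m²/day, a dose de-escalation scheme will be employed to determine the MTD below 45 mg/m²/day".
- Section 9.0, first statement: "if DLT is seen in two patients at 45 mg/m²/day, a dose de-escalation scheme will be employed".
- Section 9.0, later statement: "If two patients experience DLT at 45 mg/m²/day during the first cycle of therapy, and the toxicities are likely attributable to tretinoin".
- Section 14.1 also requires two patients at the first dose level, with no attribution condition.

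**After a first event.** Section 9.0: "A DLT in one patient at any of the three dose levels tested will require the addition of three patients at that dose level". Section 11.5 also expands the cohort at any dose level, but only when the toxicity is "attributable to tretinoin, three additional patients will be added to that dose level". Its next sentence, on a second patient, carries no attribution condition. Section 14.1 expands after one DLT in three and states that escalation continues at one in six.

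**DLT definition.** Section 11.5 defines a DLT by grade (III or IV, non-hematologic) and gives no time window. Section 14.1 uses the same grades but counts only the first cycle. Neither definition mentions attribution. Sections 1.0 and 9.0 refer to Section 11.5 for the definition. Section 9.0 also sets the treatment duration: "Patients will receive treatment for a minimum of 4 cycles, barring removal for progression of disease or excessive toxicity".

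**The concern.** Defining the MTD is part of the phase I primary endpoint in Section 2.0. The MTD fixes the tretinoin dose for phase II, and the six patients treated at it count in stage 1. The decision rule therefore has to give one answer for any set of patients. As written it does not: the next step depends on which section the study team opens.

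The first dose level is where this matters most, because only there does the choice lie between going up, adding patients and going below the planned range. The only operating characteristics in the plan, the escalation table in Section 14.1, describe one of the competing rules and say nothing about the others.

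**Working it through.** **1. The sections applied to the same data**

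| Observation | One reading | Another reading |
|---|---|---|
| One attributable DLT in the first three at 45 | De-escalate (1.0; last trigger sentence of 11.5) | Add three patients at 45 (9.0; 14.1; expansion sentence of 11.5) |
| 1/3 then 0/3 at 45, attributable | De-escalate (1.0 and 11.5 as worded) | Escalate (14.1) |
| Two DLTs at 45, neither attributed to tretinoin | De-escalate (4.2; first statement in 9.0; 14.1) | Condition not met (later statement in 9.0; 11.5) |
| One unattributed grade III/IV event in the first three, any level | Add three (9.0; 14.1) | Condition not met (11.5) |
| First grade III event arises in cycle 2 | A DLT (11.5 definition) | Not a DLT (14.1 definition) |

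Section 11.5 appears on both sides of the first row, so it contradicts itself. Section 9.0 is on both sides of the third.

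**2. Reproducing the plan's table**

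Let p be the true DLT probability. Under Section 14.1 the dose goes up after 0/3, or after 1/3 followed by 0/3:

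P(escalate) = (1−p)³ + 3p(1−p)² × (1−p)³ = (1−p)³ + 3p(1−p)⁵

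| p | .10 | .20 | .30 | .40 | .50 | .60 |
|---|---|---|---|---|---|---|
| Computed | .906 | .709 | .494 | .309 | .172 | .082 |
| Printed | .91 | .71 | .49 | .31 | .17 | .08 |

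The table is correct for the two-DLT rule with expansion to six, counting every DLT.

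**3. Comparing the two triggers at 45 mg/m²/day**

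Every DLT is taken as attributable, and the one-DLT sentences are applied as worded.

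| Quantity | Formula | p = .10 | p = .20 | p = .30 |
|---|---|---|---|---|
| Exactly one DLT in the first three (instructions differ) | 3p(1−p)² | .243 | .384 | .441 |
| 1/3 then 0/3 (final decisions opposite) | 3p(1−p)⁵ | .177 | .197 | .151 |
| De-escalate, one-DLT wording | 1 − (1−p)³ | .271 | .488 | .657 |
| De-escalate, two-DLT wording | 1 − P(escalate) | .094 | .291 | .506 |
| Move up, one-DLT wording | (1−p)³ | .729 | .512 | .343 |

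Example at p = .20: (0.8)³ = 0.512, so one-DLT de-escalation is 1 − 0.512 = 0.488. Also 3 × 0.2 × (0.8)⁵ = 0.197, so two-DLT de-escalation is 1 − (0.512 + 0.197) = 0.291. The gap between the two wordings, 0.488 − 0.291 = 0.197, is exactly the 1/3-then-0/3 case.

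**4. Attribution and window**

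The documents give no rate for either, so their effect cannot be estimated. As an illustration only, suppose that just a fraction a of DLTs counted under the Section 14.1 rule, so that p is replaced by a × p. With a total DLT rate of .30, P(escalate) would be .49, .65 and .81 for assumed a of 100%, 75% and 50%. The printed table holds only for the first.

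**The case against.** The strongest reply is that the one-DLT sentences are loose wording. Sections 1.0 and 11.5 both refer to Section 9.0 for the de-escalation schema, and Section 9.0 says two patients twice. Section 1.0 also refers to Section 14 for the escalation scheme, which says two as well. Section 11.5 expands after one event at any level and places the MTD below a dose with toxicity in at least 33% of patients. One in six is 16.7%, so 1/6 at 45 would not put the MTD below 45 on that definition. The MTD definitions in 11.5 and 14.1 agree on the count, since 2/6 (33.3%) fails both.

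This makes the two-patient reading the more natural one on the count, but it does not settle the matter. The cross-references point to a schema; they do not say that Section 9.0 overrides the trigger just stated, and no order of precedence is given. Section 9.0 never says what follows 1/6; only Section 14.1 does. Section 9.0 is also uneven on attribution, so deferring to it leaves that question open. The 33% definition shows that Section 11.5 disagrees with its own last trigger sentence.

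Two narrower points stand. The window problem is an omission, since no section states a window other than cycle 1; but the omission is in the definition that other sections cite, and two sections carry the number 11.5. The de-escalation figures for the one-DLT wording are an upper bound for Section 11.5, because that sentence requires attribution. Also, a team following that wording would not enrol the second three patients at 45, so the figures for exactly one DLT in the first three are the cleaner measure of conflicting instructions.

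**Conclusion.** The concern holds. At true DLT rates of 10%, 20% and 30%, the written triggers give different instructions at 45 mg/m²/day with probability 24%, 38% and 44%, and lead to opposite final decisions with probability 18%, 20% and 15%. These figures assume independent patients, every DLT attributable, and the one-DLT sentences taken literally. Uneven attribution and the missing window add conflicts whose size the documents do not allow one to estimate.

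The defect lies in the inconsistency between sections, not in the arithmetic of Section 14.1. It must be fixed, because the rule determines a primary endpoint and the dose carried into phase II.

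**What to change.** Reconcile Sections 1.0, 4.2, 9.0, 11.5 (Establishment of MTD) and 14.1 so that they state:
- one DLT definition;
- one observation window, included in that definition;
- one attribution rule, applied alike to first and second events, expansion and de-escalation, and covering events whose attribution is unknown;
- one trigger for leaving 45 mg/m²/day downward, and the action after 1/6 wherever the scheme is described.

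Which rule to adopt is for the investigators. Give the two sections numbered 11.5 different numbers so that the cross-reference for the DLT definition is unambiguous. If phase I decisions have already been taken, record which rule was applied to each cohort.

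The cost is a wording amendment in five sections, with no added patients or procedures. The escalation table stays if the Section 14.1 rule is kept and must be recomputed if it is not.
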